9.2 Statistical analysis methods

For continuous variables that follow a normal distribution, data will be presented as mean \pm standard deviation. For continuous variables that do not follow a normal distribution, data will be presented as median and interquartile range. Between-group comparisons will be performed using the independent t-test or Mann-Whitney U test. Categorical or ordinal data will be summarized using frequencies and percentages. For comparisons of categorical data between two groups, the χ^2 test or Fisher's exact test will be used; for ordinal data, the Mann-Whitney U test will be applied. All statistical analyses will be performed using SPSS software. A p-value < 0.05 will be considered statistically significant.

10. Study steps

After preliminary screening, patients who meet the criteria for endovascular intervention will undergo the procedure. Endovascular treatment methods include mechanical thrombectomy and aspiration.

[figure not shown]
At the end of the endovascular procedure, angiography will be used to assess successful reperfusion of the occluded vessel without in-situ or proximal arterial stenosis, with mTICI \geq 2b. Additionally, the patient's systolic blood pressure will be continuously elevated (\geq 140 mmHg, maintained for >10 minutes).

Randomization.

The intensive blood pressure control group will receive more intensive blood pressure management (target systolic blood pressure of 120 mmHg, achieved within 1 hour and maintained for 48 hours). The less intensive blood pressure control group will not have strict blood pressure control (target systolic blood pressure of 140-180 mmHg).

Follow-up and data collection.

11. Study schema

[figure not shown]

Figure 1. Study schema

12. Schedule of evaluations

Evaluation	Baseline (Prior randomisation)	Treatment phase		Follow-up phase
		1 day	7 days ^a	
Consent	X			
Eligibility	X			
Basic information	X			
Medical history	X			
Blood pressure	X	X	X	
mRS	X		X	X
NIHSS	X	X	X	
ASPECTS	X			
EQ-5D				X
Blood tests	X			
Menstrual history/urine pregnancy test (female)	X			
Electrocardiogram	X			
Details of rt-PA (if performed) and endovascular thrombectomy	X			
Brain imaging (CT ± CTA/MRI±MRA/DSA)	X	X	X	
BP lowering treatment		X	X	
Standard stroke care		X	X	X

SAEs	X	X	X	X
Complications		X	X	X
Completion status of research				X

Table 1. Experimental procedures and items to be assessed at each time point

a: Or the day of discharge (if the patient is discharged before day 7).

13. Management of adverse events during and after the study

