4.5 Privacy protection

Patients' medical records (study case records/CRFs, laboratory reports, etc.) will be securely stored at the hospital, with clinical test results well documented. Only the researchers involved in this study, the ethics committee, and regulatory authorities will be permitted to access the patient's medical records. Any public reports on the study findings will not disclose any patient identifying information. We will make every effort, within the bounds of the law, to protect the privacy of patients' medical data. In accordance with medical research ethics, except for personal privacy information, trial data will be accessible for public inquiry and sharing, limited to web-based electronic databases.

5. Sample size calculation

Based on published literature and clinical experience, the estimated 90-day functional independence rate (defined as mRS ≤ 2) in the control group is 35%. Using a two-tailed significance level of $\alpha = 0.05$, with 80% statistical power ($1-\beta = 0.8$), and a 1:1 allocation ratio between the experimental and control groups, we estimate that 376 participants per group are needed to detect a 10% improvement in the functional independence rate between groups. Considering a 20% dropout rate, a total of 910 subjects are needed to be enrolled, with 455 participants in each group.

Randomization will be performed using block randomization with block size of 10 (with at least 10 participants per center). For practical implementation, each center will be allocated a block, for example, if Center 1 plans to enroll 20 participants, blocks 1-2 will be allocated. This randomization scheme will be followed accordingly. If stratification variables are used, randomization will be performed within each stratum.

6. Randomization

Patients will be randomly assigned to two groups in a 1:1 ratio. Stratified block randomization will be used, with stratification by study center and intravenous thrombolysis. A 1:1 randomization

sequence will be generated. The randomization process will be managed using the "Jinling mouse" app.

7. Medication protocol

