8.3 Secondary efficacy outcome

mRS score 0–1 at 90 days;

mRS score 5–6 at 90 days;

Functional recovery, defined by 90-day mRS score improvement (shift analysis);

Infarct volume at 24 hours;

Change in infarct volume at 24 hours (compared to baseline);

NIHSS score at 24 hours;

Change in NIHSS score at 24 hours (compared to baseline);

24-hour NIHSS score 0–1 or improvement >8 points (%);

Change in NIHSS score at 7 days;

Brain edema volume at 7 days;

Health-related quality of life at 90 days (assessed by EQ-5D score).

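### Randomisation is stratified by centre and thrombolysis, but Section 9.2 names only unadjusted tests, which are valid yet leave available precision unused

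*Protocol*

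**What the plan says.** Section 6 fixes the design: "Stratified block randomization will be used, with stratification by study center and intravenous thrombolysis". Section 5, immediately before it, is conditional: "If stratification variables are used, randomization will be performed within each stratum".

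Section 9.2 assigns tests by type of data:

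- Categorical: "For comparisons of categorical data between two groups, the χ^2 test or Fisher's exact test will be used". The primary outcome in Section 8.1 (90-day mRS 0–2) is binary and so falls here.
- Ordinal: "for ordinal data, the Mann-Whitney U test will be applied". This covers the mRS shift in Section 8.3.
- Continuous: "Between-group comparisons will be performed using the independent t-test or Mann-Whitney U test". This covers NIHSS and infarct volume, including their changes from baseline.

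No section names a stratified test, a regression model or a covariate. The schedule in Section 12 collects basic information, NIHSS, ASPECTS and details of thrombolysis before randomisation. On sizing, Section 5 says "we estimate that 376 participants per group are needed to detect a 10% improvement in the functional independence rate between groups", from a control rate of 35%, two-sided α of 0.05 and 80% power.

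**The concern.** Stratified randomisation balances the arms within each stratum. If the strata predict outcome, the true variance of the treatment difference is smaller than an unadjusted test assumes, so the test is conservative and some power is lost. If the strata do not predict outcome, nothing is lost.

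Separately, Section 9.2 makes no use of age, baseline NIHSS or ASPECTS. Where such variables predict 90-day mRS, adjusting for them gains precision without more patients. The evaluable number was set at exactly 80% power with no margin, so that gain is worth having.

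The text also gives no single account of the strata: Section 5 leaves them open, Section 6 fixes two, and Section 9.2 uses none. Naming the adjustment set before outcomes are seen by arm removes a later choice between adjusted and unadjusted results.

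**Working it through.** **1. The plan's own figure.** Inputs from Section 5: 35% against 45% (10 percentage points), two-sided α 0.05, power 80%, allocation 1:1. With the pooled two-proportion formula and mean rate 0.40:

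n = [1.960 × √(2 × 0.40 × 0.60) + 0.842 × √(0.35 × 0.65 + 0.45 × 0.55)]² / 0.10² = 375.6, i.e. 376 per arm.

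This matches the protocol. Power at 376 is 80.05%. The sizing therefore rests on an unadjusted comparison, and the planned power does not depend on adjustment.

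**2. Adjusting for the strata alone (simulation).** From the protocol: 910 randomised and blocks of 10 within centre by thrombolysis. Assumed, because the protocol does not give them: 20 or 45 centres of unequal size, 40% thrombolysed, and the prognostic strengths below. Random loss of 17.4% leaves the 752 (2 × 376) that the sizing requires: (910 − 752)/910 = 17.4%. There were 10,000 null runs (Monte Carlo SE 0.2 points) and 6,000 power runs (SE 0.5 points) per scenario. The adjusted analysis was a risk-difference model with robust SE, for thrombolysis and centre, with centres under 10 pooled.

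| Centre SD (log-odds) / thrombolysis OR | Unadjusted type I error, 20 / 45 centres | Power, unadjusted → adjusted, 20 centres | Power, unadjusted → adjusted, 45 centres |
|---|---|---|---|
| 0 / 1.0 | 5.0% / 5.1% | 80.6 → 80.6% | 80.6 → 80.0% |
| 0.3 / 1.3 | 4.7% / 4.9% | 80.1 → 80.2% | 80.2 → 79.8% |
| 0.6 / 1.4 | 4.1% / 4.6% | 80.7 → 82.4% | 81.1 → 82.7% |
| 0.9 / 1.5 | 3.8% / 3.8% | 82.2 → 86.0% | 81.3 → 84.9% |

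Type I error of the adjusted test was 4.8–5.4%. The change in power runs from −0.6 to +3.8 points. A Mantel-Haenszel test stratified on every centre-by-thrombolysis cell, with 45 centres, gave 78.3, 78.1, 81.0 and 83.6%. It therefore loses about 2 points when the strata are weak (80.6% to 78.3%).

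A separate simulation (38 centres, 752 analysed, 4,000 runs) agreed. Unadjusted type I error was 3.9–5.2%, and the cell-stratified test changed power by about −1 to +3 points.

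**3. Adding baseline covariates.** If strata and covariates together explain a share R² of outcome variance, the standard error scales by √(1 − R²), and the equivalent saving is 376 × R² per arm. All R² values are assumptions.

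| Assumed R² | Power at 376 per arm | Equivalent saving per arm |
|---|---|---|
| 5% | 82% | 19 |
| 10% | 84% | 38 |
| 15% | 86% | 56 |
| 20% | 88% | 75 |

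Two simulations support this range:

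- A logistic model with one baseline score raised power from 79.1% to 84.2% (score SD 0.8 on the log-odds scale), and from 79.5–81.4% to 87.6–89.3% (SD 1.2).
- A logistic model with thrombolysis, pooled centre and three covariates, 752 analysed, kept type I error near 5%. With no prognostic covariate, the adjusted and unadjusted powers were within Monte Carlo noise of each other (80.0% and 80.7%). Under assumed prognostic strengths it gained about 3 to 9 points.

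**4. Change scores.** With equal variances and baseline correlation ρ, the standard error of a t-test on change relative to ANCOVA is √[2/(1 + ρ)]. This is 1.155 at an assumed ρ of 0.5 and 1.085 at 0.7, so about 15% and 8% larger. It applies only where the t-test is used and does not carry over directly to Mann-Whitney U.

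**The case against.** The strongest reply is that nothing here is wrong. The tests are valid, chi-square is the test the trial was sized on, and type I error is not inflated. Adjusting for the two strata alone does little unless centres differ strongly. The larger gains rest on R² values that appear nowhere in the protocol. Covariate lists and pooling rules usually belong in a statistical analysis plan, which is not shown. Section 9.2 also requires SPSS, and whether it conveniently delivers a random centre effect and a standardised risk difference has not been checked. The Section 5 phrase is loose drafting, since Section 6 is clear.

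Much of this stands: it is an efficiency point, the strata-only gain is small, and the Section 5 change is editorial. Two parts do not defeat the concern. First, Section 9.2 is not silent. It assigns a test to each data type, so an adjusted primary analysis in an analysis plan would depart from it. Second, the gain is uncertain in size, but the downside is small: the multi-covariate logistic model lost nothing beyond simulation noise when no covariate was prognostic.

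It is also fair to note that the simulations used 752 analysed, whereas the stated 20% dropout leaves 910 × 0.80 = 728, or 364 per arm, with 78.8% power unadjusted. That makes the precision more useful: an assumed R² of 5% or 10% gives about 80.8% or 82.8% at 364 per arm.

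**Conclusion.** The concern holds as a recommended improvement, not as an error. The unadjusted tests are valid, at worst mildly conservative (type I error down to 3.8% under the strongest assumed strata), and the planned 80% power is not lost by using them.

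What is forgone is precision. For the strata alone this is worth between −0.6 and +3.8 points of power. For strata plus baseline covariates it is about 2 to 8 points at an assumed R² of 5 to 20%. All of these depend on assumed prognostic strengths, and the strata-only range also on assumed centre numbers and thrombolysis share. That Section 9.2 ignores the strata, and that Section 5 hedges on them, can be read directly from the text.

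**What to change.** **In Section 9.2:**

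- Make the primary analysis a logistic regression of 90-day mRS 0–2 on arm, adjusted for intravenous thrombolysis, centre (a random effect, or small centres pooled by a pre-stated rule), age, baseline NIHSS and ASPECTS.
- Report the marginal risk difference with its 95% CI, so that the result is on the scale of the 10-point sizing difference, alongside the odds ratio.
- Use a proportional-odds model with the same covariates for the mRS shift, and ANCOVA on the follow-up value adjusted for baseline for NIHSS and infarct volume.
- Do not stratify on every centre-by-thrombolysis cell.
- Keep the present unadjusted tests as sensitivity analyses.

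**In Section 5:** replace the conditional sentence with the two factors named in Section 6.

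If only one change is made, adjust the primary analysis for the two stratification factors. Settle the wording before outcomes are seen by arm.

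**Cost:** text in Section 9.2 and one phrase in Section 5, with no new data. It needs pre-stated rules for sparse centres and for a missing baseline value, and somewhat more analysis work. The conditional odds ratio is not the 10-point risk difference, so a standardisation step is needed. The proportional-odds model and ANCOVA bring model assumptions that the current tests avoid. Confirm that the named software can do all this, or widen the software sentence.

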13.1 Adverse event (AE)

An AE refers to any unfavorable medical event that occurs in a participant after receiving a drug or medical device, but it is not necessarily causally related to the treatment.

13.2 Severity assessment of AEs

The intensity or severity of AEs is categorized into four levels:

- Mild: Does not affect daily activities.
- Moderate: Affects daily activities.
- Severe: Results in the loss of ability to perform daily activities.
- Serious: As defined by the serious adverse event (SAE) criteria.

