8.4 Secondary safety outcomes

Asymptomatic intracerebral hemorrhage (aSICH);

Large cerebral infarction or surgical intervention for intracerebral hemorrhage;

Complications excluding intracerebral hemorrhage (including gastrointestinal bleeding, urethral bleeding, oral or nasal mucosal bleeding, and subcutaneous hematomas);

Non-hemorrhagic severe adverse events (including brain herniation, pneumonia, respiratory failure, circulatory failure, stress ulcers, secondary epilepsy, urinary tract infections, sepsis, renal failure, acute coronary syndrome, venous thromboembolism, and psychiatric symptoms);

Procedure- or device-related complications (including arterial rupture, arterial dissection, complications at the vascular puncture site, and vasospasm).

9. Statistical analysis

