13.3 SAEs

An SAE refers to any event occurring during the clinical trial that results in:

- Death;
- Severe deterioration in the health of the patients, users, or others;
- Life-threatening illness or injury;
- Permanent impairment of bodily structure or function;
- Requirement for hospitalization or prolongation of hospitalization;
- Need for medical or surgical intervention to prevent permanent impairment of body structure or function, fetal distress, fetal death, or congenital abnormalities/defects.

Note: Hospitalization planned due to pre-existing conditions or as required by the clinical trial protocol, without significant deterioration in health, is not considered an SAE.

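### The adverse event scale puts seriousness on top of severity, so serious events get no intensity grade and the scope of the severe-event outcome is left open

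*Protocol*

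**What the plan says.** Protocol Section 13.2 opens with "The intensity or severity of AEs is categorized into four levels". The first three levels (mild, moderate, severe) are set by effect on daily activities, the third being "Severe: Results in the loss of ability to perform daily activities". The fourth level changes the basis: "Serious: As defined by the serious adverse event (SAE) criteria".

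Section 13.3 supplies those criteria. "An SAE refers to any event occurring during the clinical trial that results in" one of several listed consequences. Death comes first, and the list includes "Life-threatening illness or injury" and "Requirement for hospitalization or prolongation of hospitalization".

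Section 13.4 requires a form for each serious event, on which severity is one of the items to be recorded.

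Section 8.4 lists as a secondary safety outcome "Non-hemorrhagic severe adverse events (including brain herniation, pneumonia, respiratory failure, circulatory failure, stress ulcers, secondary epilepsy" and further conditions, among them renal failure, sepsis and acute coronary syndrome. It does not refer to Section 13.2 and does not say what severe means there.

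**The concern.** Severity describes how intense an event is. Seriousness is a regulatory classification based on consequence. An event can be mild and serious (a minor infection that delays discharge) or severe and not serious. With seriousness as the top step of an intensity scale, an event that meets a Section 13.3 criterion has no intensity grade of its own.

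Two things are at stake. First, serious events cannot be ranked by intensity, and an analysis plan written later could not recover a grade that sites never recorded. Second, the Section 8.4 outcome uses a word that Section 13.2 assigns to the level below Serious. Sites or analysts could then count different events under the same label. Circulatory failure, renal failure and acute coronary syndrome are named in this outcome and in no other listed outcome.

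**Working it through.** There is no figure to reproduce. The check sets the sections side by side.

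**Step 1: the levels are exclusive.** Section 13.2 sorts events into four levels, which implies one level per event. An event that meets any Section 13.3 criterion therefore goes to Serious and not to Severe, Moderate or Mild.

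**Step 2: the severity item on the form.** Section 13.4 asks for severity on a form used only for serious events. The only severity scale in the protocol is that of Section 13.2, under which each of these events is graded Serious. The item then has one possible value and distinguishes nothing.

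**Step 3: the Section 8.4 outcome.** The four invented events below use conditions from the Section 8.4 list. They show how the count depends on the reading. They are not rates.

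| Invented event | Level under 13.2 | Severe level only | Severe or worse | Serious was meant |
|---|---|---|---|---|
| Life-threatening respiratory failure | Serious | out | in | in |
| Mild urinary tract infection that prolongs the stay | Serious | out | in | in |
| Psychiatric symptoms that remove daily activities, no 13.3 criterion met | Severe | in | in | out |
| Pneumonia that affects daily activities, no 13.3 criterion met | Moderate | out | out | out |
| Counted, of 4 | | 1 | 3 | 2 |

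If being on the list were enough whatever the grade, all 4 would count. The protocol does not choose between these readings. The first two rows also show Step 2 at work: a life-threatening event and a mild one receive the same grade.

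**Step 4: how firm is the line between the two levels?** Section 13.3 includes a severe worsening of health among its own criteria. The third row could therefore be argued into Serious as well. The protocol does not keep the two words apart, which adds to the ambiguity.

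**Step 5: what is still captured.** All-cause mortality at 3 months is a primary safety outcome (Section 8.2). The schedule in Section 12 has serious events collected at every time point and complications at every time point after baseline.

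**The case against.** The strongest reply is that Section 8.4 never invokes the Section 13.2 scale. It names conditions such as brain herniation and sepsis, and an outcome that names these is hardly meant to leave out their life-threatening forms. On a ranked scale, severe is naturally read as severe or worse. This stands. A reader might infer that the outcome drops fatal and life-threatening events. The documents do not support that as a fact: it follows only under the strict reading, and the list suggests that something wider was meant.

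A second reply is that the data are collected anyway, and that deriving one secondary outcome can be left to an analysis plan that is not shown. This stands for the Section 8.4 count. It does not answer the grading rule in Section 13.2, which acts when the event is recorded. The form's separate severity item might mean that intensity is graded for serious events too, but the protocol offers no other scale for doing so.

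Three further inferences go too far:

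- **That this is the only outcome for the non-bleeding harms of lower pressure.** This is true only of circulatory failure, renal failure and acute coronary syndrome. The background names hypoperfusion and infarct enlargement as harms, and Section 8.3 measures infarct volume, NIHSS change and mRS 5–6, while Section 8.4 separately lists large cerebral infarction.
- **That the Severe level is unusable because patients with NIHSS up to 30 may already have lost daily activities.** The definition is causal: the loss must result from the event. Disability from the index stroke does not qualify.
- **That most of the important events would be lost.** The protocol gives no event rates, so no such proportion can be stated.

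**Conclusion.** The defect in Section 13.2 holds on the text: one scale carries two attributes, every serious event gets the same grade, and the form's severity item is uninformative. This assumes that the four levels are exclusive, as the wording implies, and that no other severity scale is in use.

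For Section 8.4 the finding is an ambiguity. Events that are fatal, life-threatening or prolong the stay fall outside the outcome only if severe is read strictly by Section 13.2.

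The consequence is minor. It is confined to one secondary safety outcome and the severity grading of serious events. The primary efficacy outcome and both primary safety outcomes are unaffected under any reading. The number of events involved cannot be estimated from the document.

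**What to change.** - **Section 13.2:** grade every event mild, moderate or severe, and record seriousness as a separate yes/no field by the Section 13.3 criteria.
- **Section 13.4:** no new item is needed. Severity on the serious adverse event form becomes informative once it uses the three-level grade.
- **Section 8.4:** define the outcome as any listed event that is graded severe or meets a Section 13.3 criterion. In the illustration this counts the same 3 of 4 events as the severe-or-worse reading, and it keeps the intensity grade of each.

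The cost is protocol wording and one extra form field, with no added visits. The change should be made at data collection, because a later analysis plan can settle the count but cannot supply missing grades.

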13.3 SAEs

An SAE refers to any event occurring during the clinical trial that results in:

- Death;
- Severe deterioration in the health of the patients, users, or others;
- Life-threatening illness or injury;
- Permanent impairment of bodily structure or function;
- Requirement for hospitalization or prolongation of hospitalization;
- Need for medical or surgical intervention to prevent permanent impairment of body structure or function, fetal distress, fetal death, or congenital abnormalities/defects.

Note: Hospitalization planned due to pre-existing conditions or as required by the clinical trial protocol, without significant deterioration in health, is not considered an SAE.

